### ***Compliance Definition***

Patients will be grouped as regular compliers (RC), erratic compliers (EC), or non-compliers (NC), as described by Monje and cols. (2017). Complete compliance will be based on the longest SPT recall interval possible for each group.

## **SPECIFIC COMMISSION OF THE DOCTORAND**

Groups:

RC = 3- to 6-month recall interval ( $\geq 2$  SPT/year)

EC = 7- to 12-month recall interval ( $< 2$  SPT/year)

NC = no recall interval program (no SPT/year)

Patients who participated in a recall schedule but discontinued SPT in future appointments will be categorized as EC or NC according to their compliance during the following years

Considering the beginning of the COVID-19 Pandemic in early 2020 and the consequent lockdown between March and May of the same year, those patients unable to come to their programmed SPT appointment due to the lockdown, but came right after the easing of the restrictions, will be considered as compliers – in a case-by-case evaluation from the authors of the study.

### **Study Visits**

#### *a) SPT visit*

One calibrated investigator will consecutively call patients for SPT visits and will be responsible of enrolling the patients ([name]).

The study variables will be recorded in a case report form (CRF) specially designed for the study. Each study patient will be assigned a numerical code comprising a 3-digit patient code (assigned correlatively as they are included in the study). Only the study investigator will be able to identify the patient by their code.

### **Screening examination**

The clinician will review with the patient the Information and Medication History Forms and record the anthropometric, socio-demographic and clinical information. Candidates will undergo an oral pathology examination and a full-mouth manual probing using a periodontal probe PCP-UNC 15 (HuFriedy®, [name]) to determine their periodontal and peri-implant status. Presence or absence of plaque will be recorded after staining with an erythrosine disclosing dye (Plac-Control®, Dentaid SL, Cerdanyola, Spain). Finally, periapical radiographs (Dürr Dental AG, Bietigheim-Bissingen, Germany) of all implants will be taken using a paralleling cone technique and a film-holder (7mA- 60kV/20ms).

The same calibrated examiner ([name]) will record clinical variables of mPI, BOP, PPD, MR and clinical attachment level (CAL).

### **Oral hygiene instructions.**

Individualized instructions in proper oral hygiene measures will be given to all patients ([name]) enrolled in the study. Patients will be instructed to brush their teeth and implants twice daily to remove bacterial plaque with

## **SPECIFIC COMMISSION OF THE DOCTORAND**

a low-abrasive dentifrice and to use specific cylindrical or conical brushes in the interproximal area. Patients will be indicated to brush under, around, and in the peri-implant crevice circumferentially. In those cases with no access for the interdental brush, patients will be instructed to use a floss threader or a specialized floss that has a built-in threader (Super Floss®, OralB®, Procter & Gamble, Cincinnati, OH, USA) and to wrap in a circle and move into the peri-implant crevice.

### **Randomization and study groups**

Once oral hygiene instructions were provided, patients will be randomly assigned to the Test or Control groups. Allocation of patients will be decided following randomization tables with permuted blocks of four while the information will be concealed by using opaque envelopes, which will be labelled with the patient study number and only be revealed after oral hygiene instructions are provided.

### **Debridement**

All the supragingival debridement will be performed by the residents of the Master's Program in Periodontology at CUO – UIC (Sant Cugat del Vallès). Subjects will receive a session of full-mouth professional prophylaxis with:

- Control group: an ultrasonic device (DTE-D5, Woodpecker®, Guilin, China) with a plastic tip (Hu-Friedy®, [name], USA) and scaling with plastic curettes (Hu-Friedy®, [name], USA) around dental implants and a conventional metal tip for teeth will be used.

- Test group: an erythritol based air-polishing powder (Air-Flow, EMS, Nyon, CH) during 5 seconds on each site (Schwarz et al., 2015).

In those cases where implant-supported restorations do not facilitate oral hygiene access, the modification of the implant prosthesis in order to facilitate oral hygiene access will be performed using the protocol described in de Tapia et al., 2019.

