#### b) Specific objective

1. To evaluate pain/discomfort during SPT around dental implants and teeth.
2. To evaluate patient reported outcomes and clinical variables by decontamination during SPT with erythritol based air polishing powder (Air Flow Master®, Air-Flow Plus®, EMS, Nyon, Switzerland), at the first SPT and after 2 years.
3. To evaluate the effect of erythritol based air polishing powder (Air Flow Master®, Air-Flow Plus®, EMS, Nyon, Switzerland) during SPT on the compliance rates after 1 and 2 years of follow-up.

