#### b) Specific Hypothesis

1. SPT with conventional ultrasonic device will result in more pain/discomfort around dental implants than in teeth.
2. SPT by means of an erythritol based air-polishing powder (Air Flow Master®, Air-Flow Plus®, EMS, Nyon, Switzerland) will result in better patient reported outcomes and same clinical outcomes, at the first SPT and after 2 years.
3. SPT by means of an erythritol based air-polishing powder (Air Flow Master®, Air-Flow Plus®, EMS, Nyon, Switzerland) will result in the increase of the compliance rates after 2 year of follow-up.

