### **VAS**

After finishing the supragingival debridement around teeth, another calibrated examiner ([name]) will give the patients graded pain intensity on a visual analogue scale (VAS) (0 = no pain and 10 = extreme, unbearable pain), and then perform supragingival debridement around the dental implants and give VAS again. Patients will be instructed to point at the VAS.

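### Hypothesis 1 compares pain at implants and teeth in an arm that uses different instruments at the two sites, and no paired site contrast is prespecified in either arm

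*Combined protocol and SAP*

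**What the plan says.** Specific Objective 1 is not tied to an arm: "To evaluate pain/discomfort during SPT around dental implants and teeth". Specific Hypothesis 1 is tied to one modality: "SPT with conventional ultrasonic device will result in more pain/discomfort around dental implants than in teeth". That modality is the control treatment.

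The Debridement section applies to everyone ("Subjects will receive a session of full-mouth professional prophylaxis with") and then describes each arm:

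- **Control, implants:** ultrasonic device with a plastic tip, and "scaling with plastic curettes".
- **Control, teeth:** a metal tip. The sentence joins the two sites as "around dental implants and a conventional metal tip for teeth will be used".
- **Test:** erythritol air-polishing "during 5 seconds on each site", with no stated distinction between teeth and implants.

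The VAS section takes two ratings per patient, with no restriction by arm. The first follows the teeth ("After finishing the supragingival debridement around teeth, another calibrated examiner" hands over the scale). The same sentence continues "then perform supragingival debridement around the dental implants and give VAS again".

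Under Inferential analysis, VAS is the main outcome and data are to be handled at patient level and at implant/tooth level. The tests listed are Student's t, Fisher's exact, ANOVA, regression or correlation, and their non-parametric counterparts. None is identified as paired, and no implant-versus-tooth contrast is described. The difference in instruments between the two sites is not acknowledged anywhere.

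**The concern.** Hypothesis 1 names one device at two sites, but the control arm delivers a different instrument set at each. The curette step exists only at implants and the metal tip only at teeth. A positive result could reflect the site, the added curettes or both. A null result could reflect a real site difference offset by the plastic tip. The documents give no basis for the size or direction of the instrument effect.

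This matters because the introduction's reasons for expecting more pain around implants are properties of the site: different tissues, or more inflammation. A reader of the results would naturally take a positive control-arm finding as support for those reasons, and the control-arm data cannot give that support. VAS is the main outcome and this is the first of three specific hypotheses, so the result will be prominent.

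**Working it through.** **1. The plan's own number.** The sample size is built on change in clinical attachment level (CAL), with difference 1 mm, SD 0.9, alpha 0.05 (two-sided assumed, since sidedness is not stated), power 80% and 12% loss.

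- n per arm = 2 × (1.960 + 0.842)² × 0.9² / 1² = 12.7, so 13.
- 13 / (1 − 0.12) = 14.8, so 15 per arm and 30 in total.

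This reproduces the stated 30. It concerns a between-arm CAL difference and does not bear on the implant-versus-tooth VAS comparison.

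**2. What each arm's difference contains.** Let S be the effect of site (implant minus tooth), I the effect of plastic tip plus curettes relative to the metal tip, and O the effect of being treated and rated second. Each patient gives one VAS for teeth and one for implants.

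| Arm | Teeth (first) | Implants (second) | Expected implant − tooth difference |
|---|---|---|---|
| Control | metal tip | plastic tip + plastic curettes | S + I + O |
| Test | air-polishing | air-polishing (if the per-site rule covers both) | S + O |

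If a different operator treats the implants, an operator term joins both rows.

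**3. Can the terms be separated?** This was checked as the rank of the design matrix.

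- Control arm only, with intercept, site and instrument: rank 2 of 3. Site and instrument are not separable. As an illustration with O = 0, a control difference of 1 VAS point fits S = 1, I = 0; S = 0, I = 1; or S = 2, I = −1 equally well.
- Both arms, with intercept, site, plastic tip/curettes and air-polishing: rank 4 of 4. All are estimable if the site effect is the same under every device.
- Both arms with order added: rank 4 of 5. Site remains aliased with order.

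**4. The between-arm contrast.** (S + I + O) − (S + O) = I. This equals the instrument effect only if S does not depend on the device and any order or operator effect is the same in both arms. Without those assumptions it still shows how far the implant-tooth gap differs between the two instrument protocols.

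**5. Precision (t-based, two-sided 0.05, 80% power).**

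| Patients per arm | Paired difference within one arm | Between-arm contrast of differences |
|---|---|---|
| 15 | 0.78 SD | 1.06 SD |
| 13 (after 12% loss: 15 × 0.88 = 13.2) | 0.85 SD | 1.15 SD |

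Here SD is that of the within-patient difference, assumed equal in the two arms for the last column. The documents do not give it, so these figures cannot be converted to VAS points.

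**The case against.** **Hypothesis 1 names the treatment, so it can be read as comparing conventional care as given at each site.** On that reading it is answerable, and it fits the trial's interest in patient experience and adherence. The tissue and inflammation explanations are offered tentatively, about probing pain, and are not a mechanism the trial sets out to test. This stands in part. The package comparison is legitimate, but the hypothesis has to say that it is one. As worded it names a single device, and nothing warns the reader that the instruments differ.

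**A reader might infer that the test-arm data are excluded from this question.** The documents do not support that. Objective 1, the VAS procedure and the implant/tooth-level analysis are not limited to an arm, and a directional hypothesis about one modality does not define an analysis set. The gap is that no paired contrast is specified in either arm.

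**A reader might infer that the test arm isolates the implant effect.** It does not. Teeth are always treated and rated first, so site and order coincide in both arms. The VAS section can also be read as having the second examiner debride the implants, whereas the Debridement section gives all debridement to residents, so operator may differ by site too. In addition, it is plausible but not explicit that the five-second rule applies to teeth and implants alike.

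These limits restrict what the test arm can show. They do not rescue the control-arm inference, which shares the order problem and carries the instrument difference as well.

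**Conclusion.** The concern holds for the inference from Hypothesis 1. In the control arm, site and instrument are completely confounded in all 15 planned patients, and neither adjustment within that arm nor a larger sample can separate them. The control-arm difference describes the conventional protocol as delivered at each site. It cannot be attributed to the implant.

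The test-arm difference is free of the instrument change, provided air-polishing is applied the same way at both sites, but it remains confounded with order and possibly with operator. Reading the between-arm contrast as a pure instrument effect assumes that the site effect does not depend on the device.

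Two stronger conclusions might be drawn and are not supported. One is that a positive control-arm result would be due to the curettes; the direction of the instrument effect is unknown. The other is that the trial's main comparison is undermined; the randomised comparison of VAS between arms is unaffected by this point. The change should be made, but the trial does not depend on it.

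**What to change.** 1. Reword Hypothesis 1 as a comparison of the conventional protocol as delivered at each site: plastic tip plus plastic curettes at implants, metal tip at teeth.
2. Prespecify the within-patient implant-minus-tooth VAS difference, with a paired analysis, in each arm. Identify the test-arm difference as the one free of the instrument change, and confirm that the five-second rule covers teeth and implants alike.
3. Report the between-arm contrast of these differences with its confidence interval, as showing how far the implant-tooth gap depends on the instrument protocol. State the no-interaction assumption needed to read it as an instrument effect.
4. State as a limitation that teeth are always treated and rated before implants, in both arms. Reconcile the Debridement and VAS sections on who debrides the implants.

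The cost is some wording and one additional analysis of scores the VAS procedure already collects. Instruments, visits and care do not change. The downside is a narrower claim from the control arm, and wide intervals with about 15 patients per arm.

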### **VAS**

After finishing the supragingival debridement around teeth, another calibrated examiner ([name]) will give the patients graded pain intensity on a visual analogue scale (VAS) (0 = no pain and 10 = extreme, unbearable pain), and then perform supragingival debridement around the dental implants and give VAS again. Patients will be instructed to point at the VAS.

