## SPECIFIC COMMISSION OF THE DOCTORAND

missing or inadequate information given to patients after finishing the active periodontal treatment or the dental implant therapy is condemned to end. Patient motivation, nevertheless, is something external and depends mainly on patients' psychological factors and personality traits (Komarraju et al., 2009). The main reason is going to be addressed in the first part of this research project. The second most frequent reason for patients to fail SPT on these questionnaires was **bad experiences and dissatisfaction**. It has been demonstrated that peri-implant probing, even in healthy tissues, caused significantly more pain/discomfort than periodontal probing (Ringeling et al., 2016; Stanner et al., 2017; Parvini et al., 2017). Such finding might be due to: 1) differences between periodontal and peri-implant tissues or, 2) on average, higher levels of inflammation are observed around dental implants than around teeth (Meyer et al., 2017).

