### ***Sample Size Calculation***

The sample size will be calculated using changes in CAL as the primary outcome variable. Thirty patients (15 subjects in each group) were necessary to detect a difference of  $\geq 1$  mm in CAL assuming a mean standard deviation (SD) of 0.9. This calculation assumes an alpha error of 0.05, a beta error of 0.2, and a statistical power of 80%. In addition, 12% of loss to follow-up was considered.

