### ***Outcomes of the study***

#### **Main outcome;**

- Patient Pain/Discomfort (VAS) reported after decontamination during SPT.

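### With no VAS reading between probing and debridement at the first SPT visit, residual probing pain cannot be separated from debridement pain in the implant-versus-tooth contrast of Hypothesis 1

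*Combined protocol and SAP*

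**What the plan says.** The subsections that follow the SPT visit heading under Study Visits run in this order: screening examination, oral hygiene instructions, randomisation, debridement, VAS.

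- **Screening examination:** "Candidates will undergo an oral pathology examination and a full-mouth manual probing", which covers both periodontal and peri-implant status. Clinical Parameters adds that implant probing depth is taken at six aspects of each implant.
- **Randomization and study groups:** the envelope is opened after hygiene instruction, so after probing.
- **VAS:** "After finishing the supragingival debridement around teeth, another calibrated examiner" gives the patient the 0 to 10 scale. The implants are then debrided and the scale is given again. Patients are told to point at the scale. The section does not say which part of the visit they are to rate.
- **Main outcome:** "Patient Pain/Discomfort (VAS) reported after decontamination during SPT".
- **Specific Hypothesis, item 1:** with the conventional ultrasonic device, pain will be greater at implants than at teeth.
- **Background on compliance with SPT:** "peri-implant probing, even in healthy tissues, caused significantly more pain/discomfort than periodontal probing".

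No VAS before debridement is described, and no waiting time after probing is given.

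**The concern.** The protocol names a source of pain that differs by site, places it ahead of the outcome and does not measure it. Hypothesis 1 compares two sites within the same control-arm patients, so randomisation gives it no protection. If some probing pain persists or is remembered when the patient scores, and it follows the pattern described in the background, it adds more to the implant score than to the tooth score. That is the direction the hypothesis predicts. A positive result could then not be attributed to the debridement method rather than to the probing before it.

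The comparison between test and control arms is in a different position. At the first visit every patient is probed before allocation, so any residual is balanced in expectation. What remains is patient-to-patient variation in the main outcome, part of which a pre-debridement reading could remove.

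**Working it through.** **1. The plan's own figure.** The Sample Size Calculation section states "Thirty patients (15 subjects in each group) were necessary to detect a difference of" at least 1 mm in clinical attachment level (CAL), with SD 0.9, alpha 0.05, power 80% and 12% loss. Sidedness is not stated; two-sided is assumed.

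- n per arm = 2 × (1.96 + 0.84)² × 0.9² / 1² = 12.7, so 13.
- With 12% loss: 13 / 0.88 = 14.8, so 15 per arm and 30 in total. The figure reproduces.

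This calculation concerns CAL ("The sample size will be calculated using changes in CAL as the primary outcome variable"), not VAS, so it neither supports nor weakens the present point. It supplies the control-arm size of 15, or about 13 after 12% loss (15 × 0.88 = 13.2).

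**2. What each comparison contains.** Write each score as debridement pain D plus residual probing pain R, at implants (I) and teeth (T).

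- Hypothesis 1, control arm: mean difference = (D_I − D_T) + (R_I − R_T). The second bracket is not measured. It is zero if nothing persists or if the residual is equal at both sites, and positive if the background's pattern persists.
- Between arms, at either site: R has the same expectation in both arms because probing precedes randomisation, so it cancels on average. Its variance stays.

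**3. How much residual would matter for Hypothesis 1.** Suppose D_I = D_T, and let c be the mean of (R_I − R_T) in units of the SD of the paired difference. The chance that a two-sided 5% paired t-test declares implants more painful is the upper tail of a noncentral t with n − 1 degrees of freedom and noncentrality c√n. For n = 15 and c = 0.25 the noncentrality is 0.25 × 3.87 = 0.97.

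| c (assumed) | n = 15 | n = 13 |
|---|---|---|
| 0 | 2.5% | 2.5% |
| 0.1 | 5.5% | 5.2% |
| 0.25 | 14.5% | 12.9% |
| 0.5 | 43.8% | 38.2% |
| 1.0 | 94.9% | 91.1% |

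The documents give no VAS standard deviation. If the SD of the paired difference were 2 points (an assumption), c = 0.25 would be a residual difference of 0.5 point and c = 0.5 a difference of 1 point.

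**4. Precision between arms.** Adjusting for a pre-debridement score with correlation r multiplies the residual variance by 1 − r², apart from one degree of freedom.

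- r = 0.5: variance falls by 25%; 15 / 0.75 = 20 effective patients per arm.
- r = 0.7: variance falls by 49%; 15 / 0.51 = 29 effective patients per arm.
- r = 0: no gain.

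These correlations are assumptions; the documents give none.

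**The case against.** **Carry-over is an inference.** A reader might infer that probing pain does carry into the scores. The background says only that probing hurts more at implants. It says nothing about how long the pain lasts. Hygiene instruction, envelope opening and tooth debridement all come between probing and the implant score. The implant score is also further from probing than the tooth score, so fading would reduce the implant residual more. This stands: c = 0 is not excluded.

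**Probing as a large share of the score.** A reader might suppose that supragingival debridement is the gentler procedure and that probing therefore dominates the VAS. The documents do not say so. The background describes conventional instrumentation around teeth as less comfortable than air polishing, and the control arm receives conventional instrumentation. This premise is not used here.

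**The target may be the whole visit.** Objective 1 speaks of pain during SPT, and part of the rationale is that the visit is a bad experience. On that reading probing belongs to what is measured. This is arguable. However, Hypothesis 1 is tied to the ultrasonic device and the main outcome to decontamination, so a result framed that way needs the two sources distinguished.

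**Instructions may exist elsewhere.** Section 2.5 promises a guidebook that standardises questionnaires, and scoring after each debridement segment already directs attention to that segment. Both soften the gap, but neither supplies the instruction in the protocol.

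**A change score could over-correct.** If probing hurt 1 point more at implants but had faded by the later rating, testing the difference in change would subtract a point that was never in the later score, biasing Hypothesis 1 down by 1. Patients who already rate only debridement would likewise be corrected twice. This stands, and it is why the fix does not use a change score as the main test.

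**'Same visit' is read from the headings.** No sentence states it, although nothing places screening on another day. The order is shown for the first visit only; Follow-up visits does not say whether probing comes before debridement.

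**Conclusion.** The point holds for Hypothesis 1 at the first SPT visit. The plan cannot separate residual probing pain from debridement pain, and any residual that followed the site pattern in the background would favour the hypothesis. The size is unknown. The false-positive chances above run from 2.5% with no residual to 43.8% at half an SD with 15 patients. They assume no true debridement difference and a paired t-test, and the documents supply no value within that range.

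A reader might go further and infer that the main outcome as a whole is biased. The documents do not support that: probing precedes allocation, so the first-visit between-arm VAS comparison is unbiased on this account and can only be noisier.

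This is a cheap improvement worth making before enrolment, since a missing pre-debridement reading cannot be recovered later. It does not show that the trial's conclusions would be wrong.

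**What to change.** 1. In the VAS section, add an instruction that at each reading the patient scores only the debridement just completed at that site.
2. Add one VAS for teeth and one for implants after probing and hygiene instruction, immediately before debridement and before the envelope is opened.
3. In Inferential analysis, compare first-visit VAS between arms in a linear model with arm and the pre-debridement VAS for the same site as covariate, specified in advance.
4. For Hypothesis 1, keep the implant-minus-tooth difference in post-debridement VAS as the main test. As a sensitivity analysis, regress that difference on the pre-debridement implant-minus-tooth difference and report the estimate at a pre-debridement difference of zero. If probing pain has faded, the slope should be near zero and the estimate stays close to the main one; a change score would impose a slope of one. With about 15 control patients this estimate will be imprecise and should be read only as a check.

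The cost is two extra marks per patient on the existing scale, with the same staff and one covariate. The downside is that patients score the scale two more times.

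This does not deal with the fixed order in the VAS section, where teeth are always debrided and scored first and implants second. That order confounds site with sequence in Hypothesis 1, needs no assumption about lingering pain, and should be acknowledged separately.

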## **5. Materials and Methods:**

### ***Study Design***

The present research project is designed as a randomized controlled double-blind clinical trial with a 2-year follow-up. The reporting of this clinical trial will follow the Consolidated Standards of Reporting (CONSORT) guidelines. It is registered in ClinicalTrials.gov (...)

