#### *Inferential analysis*

Data will be calculated at patient level and implant/tooth level. VAS score will be considered as the main outcome (quantitative).

If the distribution is normal, the following tests will be used:

- Binary categorical variables: T-Student / Fisher's exact test;
- Categorical variables with > 2 categories: ANOVA;
- Quantitative variables: Simple linear regression / Pearson correlation coefficient.

If it doesn't follow normality:

- Binary categorical variables: U of Mann-Whitney;
- Categorical variables > 2 categories: H of Kruskal-Wallis;
- Quantitative variables: Spearman's correlation coefficient.

[figure not shown]

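### The main-outcome pain score is taken by having the patient point at a scale, which leaves no mark to re-measure, and nothing in the plan keeps the reading of that gesture independent of allocation

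*Combined protocol and SAP*

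**What the plan says.** The Outcomes section names one main outcome: "Patient Pain/Discomfort (VAS) reported after decontamination during SPT". The Inferential analysis section repeats it: "VAS score will be considered as the main outcome (quantitative").

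Collection is described only under VAS. After the teeth are debrided, "another calibrated examiner" gives the patient "graded pain intensity on a visual analogue scale (VAS) (0 = no pain and 10 = extreme, unbearable pain"). The same sentence continues: "and then perform supragingival debridement around the dental implants and give VAS again". The section ends: "Patients will be instructed to point at the VAS".

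Three other places bear on who reads the scale:

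- **Debridement:** "All the supragingival debridement will be performed by the residents of the Master's Program in Periodontology".
- **Study Design:** the trial is a "randomized controlled double-blind clinical trial with a 2-year follow-up". The blinded roles are not listed.
- **Follow-up visits:** an examiner is called blinded, but only for the clinical variables.

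Section 2.5 (Clinical and VAS examination) promises a case report form and a procedural guidebook. It does not say who enters the VAS value, how finely it is read, or whether the patient makes any mark.

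**The concern.** A pointed answer has to be turned into a number by someone, and once the hand moves away there is nothing left to measure again. For a secondary variable this might not matter much. Here it is the outcome on which the comparison of devices rests.

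The arms use visibly different equipment (air polishing against an ultrasonic tip with curettes), and the VAS is given during the treatment session. Specific hypothesis 2 also states an expected direction: better patient-reported outcomes with air polishing. If the reader knows the device, small and unintended differences in how an ambiguous position is read could favour one arm. Nothing would remain from which to detect or correct this.

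**Working it through.** **1. What is established and what is inferred.** Pointing is stated. That it leaves no mark follows from the method. That someone other than the patient records the value is a natural inference, but the recorder is not named. The VAS examiner's exposure to the device depends on which section is followed:

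- Under the literal wording of the VAS section, that examiner treats the implants and so handles the allocated device.
- Under the Debridement section, residents treat, and the examiner gives the scale between the two parts of one session.

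On neither reading does any sentence keep the VAS reading unaware of allocation.

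**2. The plan's own figure.** The Sample Size Calculation section uses change in CAL: difference 1 mm, SD 0.9, alpha 0.05 (two-sided assumed), power 80%, loss 12%.

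- n per arm = 2 × (1.96 + 0.84)² × 0.9² / 1² ≈ 12.7, rounded up to 13.
- 13 / (1 − 0.12) = 14.8, rounded up to 15 per arm, 30 in total.

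The stated 30 reproduces. It supplies the 15 per arm used below but says nothing about VAS, for which the documents give no SD. Every VAS SD below is therefore an assumption. The lowest, 0.9, simply borrows the CAL number as a small value.

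**3. Rounding to whole numbers.** This adds variance of about 1/12, so the new SD is √(SD² + 1/12).

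| Assumed SD | SD after rounding | Rise in SD | Rise in required n |
|---|---|---|---|
| 0.9 | 0.945 | 5.0% | 10.3% |
| 1.5 | 1.528 | 1.8% | 3.7% |
| 2.0 | 2.021 | 1.0% | 2.1% |
| 2.5 | 2.517 | 0.7% | 1.3% |

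A simulation with skewed (gamma) scores capped at 10, Mann-Whitney, 15 per arm and 8,000 trials per scenario agrees:

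- Means 2 against 1 (SD 1.5 and 1): power falls from 63% to 60%.
- Means 3 against 1.5 (SD 2 and 1.5): from 71% to 69%.
- Means 1 against 0.5 (SD 1 and 0.6): from 40% to 34%.

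Rounding costs little unless pain is very low.

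**4. A reading that differs between arms.** Suppose there is no true difference, but readings shift by a total of s points between arms. The two-sided 5% t test (28 degrees of freedom, critical value 2.048) then has noncentrality s / (SD × √(2/15)). For s = 0.5 and SD 1.5 this is 0.5 / (1.5 × 0.365) = 0.91. The false-positive rates, against a nominal 5%, are:

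| Assumed SD | s = 0.25 | s = 0.5 | s = 1.0 |
|---|---|---|---|
| 0.9 | 11.4% | 31.2% | 83.6% |
| 1.5 | 7.3% | 14.3% | 42.2% |
| 2.0 | 6.3% | 10.1% | 26.2% |
| 2.5 | 5.8% | 8.3% | 18.5% |

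With 13 per arm, the 0.5-point results at SD 1.5 and 2 are 12.9% and 9.4%.

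If the shift arises only from directional rounding, 1 point is the ceiling: every score rounded up in one arm (+0.5 on average) and down in the other (−0.5). A 0.5-point shift is half of that.

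**The case against.** The strongest reply is that much of this rests on silence. The plan does not name the recorder or forbid a mark, and the planned guidebook is where reading rules would naturally sit. The trial is called double-blind. If the VAS reader were in fact kept unaware of the device, the main harm would disappear even with pointing. The false-positive rates follow from an assumed shift and an assumed SD; they are not evidence of bias.

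Much of that stands. The recorder is inferred, and the rates are conditional illustrations. But the guidebook and case report form, as described, do not change a response method that the protocol states outright, and a form entry of a pointed position still cannot be re-measured. The double-blind label names no roles, and the only blinded examiner is assigned to other variables.

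Three stronger readings are tempting and are not supported:

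- **That the scale has printed gradations, so scores will be whole numbers.** The word graded describes pain intensity. Only two end anchors are given, and no reading resolution is stated.
- **That the reader certainly saw the device.** This depends partly on the conflict between the VAS and Debridement sections.
- **That the implant rating is anchored on the tooth rating in a way that biases the arms.** Whether the same sheet is reused is not stated, and the order of teeth then implants is the same in both arms.

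**Conclusion.** The point holds in a limited form. The main outcome is collected by a method that leaves no record open to re-measurement, from an examiner not stated to be blinded, and no sentence protects the reading from knowledge of allocation. Loss of precision from rounding is minor.

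The risk that matters is differential reading. At 15 per arm and an assumed SD of 1.5 to 2 points, a hypothetical 0.5-point total shift takes the false-positive rate from 5% to about 10-14%. A reader might infer that the pain result will be biased or that the scores are invalid. The documents support neither; they show an avoidable exposure. Because a better method is cheap and the variable is the main outcome, the change should be made rather than left to the guidebook.

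**What to change.** Replace the last sentence of the VAS section with wording such as: *The patient marks the VAS line personally, on one sheet for teeth and a separate sheet for implants, each labelled with the study code only. Staff without access to the allocation measure the distance from the zero anchor later.* The blinded clinical examiner could do the measuring. State the line length, so that the score is 10 × distance / length, and keep the sheets as source documents.

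Separately, reconcile the VAS and Debridement sections on who debrides the implants, and list the blinded roles behind the double-blind statement.

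The cost is two paper sheets and a short measurement per patient at each visit where VAS is taken (30 × 2 = 60 sheets per round), plus a slightly longer visit and some data entry. The sample size does not change. This removes the reader's influence only; it does not remove bias from patients who can tell which device was used on them.
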